3.5.2. DISCONTINUED PATIENTS

Any patient may voluntarily discontinue the study at any time without prejudice. The investigator may discontinue a patient from the study at any time if (s)he considers that remaining in the study compromises the patient's health or the patient is not sufficiently cooperative. In either event, reason(s) for discontinuation should be recorded on the CRF.

Possible reasons for study discontinuation include the following:

- AEs necessitating discontinuation from the study (pre-treatment).
- The patient is lost to follow-up.
- Patient decision (specify).
- Investigator decision (specify).
- Other reason (specify).

The reasons for any patient discontinuation will be recorded on the study completion form of the CRF.

Discontinued patient(s) will be replaced in any treatment arm if discontinuation occurs prior to the 90 Day follow-up;

Patients discontinued for AE(s) will be followed-up after patient's discontinuation until the event is resolved or considered medically stable by the investigator.

Subjects that withdraw prior to study completion will undergo the following if possible:

- Retinal Fundoscopy
- Concomitant Medications
- Serum Chemistry and hematology
- Photograph and measurement of ulcer(s) if present at baseline
- Vital Signs
- Serum HGF if discontinued prior to Day 90
- Copies of VM202 in whole blood if discontinued prior to Day 90
- Injection site reaction assessment if discontinued prior to Day 49
- Adverse Events

In case of a patient lost-to-follow-up, the investigator must do his/her best to contact the patient (by phone or letter) at least twice. If no response is obtained from the patient, the investigator is encouraged to contact one of the patient's relatives or his/her general practitioner. The evidence of these contacts must be recorded in the patient medical chart. It can be, for instance, the acknowledgement of receipt of a letter sent to the patient.

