Appendix 1. Schedule of Evaluations and Visits

SCHEDULE OF EVALUATIONS AND VISITS

PROCEDURE	Screening / Baseline (-60 – 0 D)	1 st Injection Day 0		2 nd Injection Day 14 ± 3 D		3 rd Injection Day 28 ± 3 D		4 th Injection Day 42 ± 3 D		Day 49 ± 3 D	Day 90 ± 7 D	6 mo ± 1 mo	9 mo ± 1 mo	12 mo ± 1 mo	Early Withdrawal
		Pre- dose	Post- dose	Pre- dose	Post- dose	Pre- dose	Post- dose	Pre- dose	Post- dose						
Baseline Evaluation															
Informed Consent	✓														
Complete Medical History	✓														
Complete Physical Exam	✓														
Cancer screening [†]	✓														
Viral screening – HIV, HTLV, HBV, HCV	✓														
Urinalysis	✓														
ECG	✓														
Pregnancy test	✓														
Safety and Efficacy Parameters															
Retinal Fundoscopy	✓													✓	✓
Vital Signs	✓	✓	✓	✓	✓	✓	✓	✓	✓	✓	✓	✓	✓	✓	✓
Concomitant Medications	✓	✓		✓		✓		✓		✓	✓	✓	✓	✓	✓
Serum Chemistry and hematology	✓	✓		✓		✓		✓		✓	✓	✓	✓	✓	✓
Copies of VM202 in whole blood		✓	✓**					✓	✓**	✓	✓	✓			✓ ¹
Serum HGF		✓						✓		✓	✓				✓ ¹
Visual Analog Scale (VAS) score	✓	✓		✓		✓		✓			✓	✓	✓	✓	
VascuQol		✓									✓		✓	✓	
ABI & TBI	✓	✓				✓					✓	✓	✓	✓	
TePO ₂	✓	✓										✓	✓	✓	
Photograph and measurement of ulcer(s) ^{††}	✓	✓		✓		✓		✓		✓	✓	✓	✓	✓	✓
Rutherford Classification	✓											✓	✓	✓	
MRA (at designated site(s) only) ^{†††}		✓										✓	✓		
Treatment															
Injection site reaction assessment			✓	✓	✓	✓	✓	✓	✓	✓					✓ ²
Adverse Events			✓	✓	✓	✓	✓	✓	✓	✓	✓	✓	✓	✓	✓

† Includes: cancer markers (carcinoembryonic antigen (CEA), alpha fetoprotein (AFP), CA19-9, and CA125 (females only)); chest X-ray or CT scan of the chest (if patient has a previous history of tobacco use, a CT scan will be performed instead of the chest X-ray) within 3 months; pap smear and mammogram if not performed within past 12 months (females only); PSA (males only); for patients ≥ 50 years old, colonoscopy within past 10 years

†† If present prior to first study drug administration

††† 7 days prior to Day 0; ±7 days to Month 6 and Month 9

** 2 hours after injection (± 1 hour)

1 If withdrawal occurred before Day 90 Visit

2 If withdrawal occurred before Day 49 Visit

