10.1. Primary Efficacy Variable

Subjects will be asked to assess the level of pain they feel by placing a perpendicular line on a scale of 0 (No Pain) to 100 (Pain as bad as it can be) at each visit. The subject's Visual Analogue Scale (VAS) score will be determined by where the subject places the perpendicular line by two independent readers. The average scores from the two readers will be used as the pain score for the corresponding subject. If a score is reported by only one reader, then that score will be assigned as the pain score. The primary efficacy endpoint is the change in pain level between baseline and the 9-month follow-up as determined by VAS. The change in pain will be calculated for each subject as follows:

$$\text{Change} = 9\text{-month VAS} - \text{Baseline VAS}$$

Since higher VAS indicates worse pain, a negative value of change means an improvement, and a positive value of change means deterioration.

The mean change in pain will be compared among the three treatment groups. The statistical null and alternative hypotheses for the primary efficacy endpoint are:

$$\begin{aligned} H_0: \mu_H &= \mu_L = \mu_P \text{ and} \\ H_a: \text{at least one of the three } \mu's &\text{ is different,} \end{aligned}$$

where μ_H , μ_L , and μ_P are mean change in pain from baseline to 9-month follow-up for VM202 high dose, VM202 low dose, and placebo groups, respectively.

One-way Analysis of Variance (ANOVA) with treatment (VM202 high dose, VM202 low dose, and placebo) as the factor will be used to compare the mean change in pain among the three treatment groups. Dunnett's test will be used to compare the mean change in pain level between VM202 high dose to placebo and between VM202 low dose to placebo. This analysis will be repeated using Percent (%) Change from Baseline, where Percent Change from Baseline is defined as:

- % Change from Baseline = [(9 month VAS – Baseline VAS)/Baseline VAS]* 100

An additional set of analyses will be run using non-parametric tests as described in Section 5.2 for continuous variables.

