10.1.2. Imputation Methods of VAS Results for the ITT Population

In order to include all subjects in the ITT population, the following imputation rules will be applied for analysis of the ITT population.

For subjects without the primary efficacy endpoint (VAS change from baseline to 9 months), the following imputation methods will be applied:

- For missing Baseline VAS, assign the VAS score at Screening if the VAS score at Day 0 is missing.
- For missing 9 month VAS, assign the 12 month VAS score if the 9 month VAS is missing.

- For missing 9 month VAS, assign the last reported VAS prior to the 9 month VAS visit if both the 9 month and 12 month VAS assessments are missing.

For subjects who had a major amputation or limb procedure carried out, the following imputation methods will be applied:

- For subjects with a major amputation, assign the post baseline VAS score prior to the amputation.
- For subjects with a limb salvage, assign the post baseline VAS score prior to the intervention.

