11.5. Retinal Fundoscopy

A retinal fundoscopy of each eye will be performed at Screening and at 12 Months. In the case of an early withdrawal, a retinal fundoscopy may be performed prior to 12 Months. Each eye will be given one of the following assignments: Normal, Abnormal-Not Clinically Significant, and Abnormal-Clinically Significant. Shift tables will be provided to assess changes in retinal fundoscopy. Shift tables will summarize changes from Screening to 12 Months. If a 12 Month assessment was not performed, the last post-baseline assessment reported will be used. For each of the three treatment groups, counts and percentage of subjects will be calculated for each of the 9 possible “shift” outcomes.

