^[1] Baseline defined as the last non-missing value prior to first dose of study drug.

^[2] Change = Change from Baseline

path\t_program.sas date time

Programmer Note Repeat for all available time points and vital signs.

Table 21
Retinal Fundoscopy- Shift from Baseline
Safety Population

	Screening/Baseline								
	Placebo (N=)		VM202- 8 mg (N=)		VM202- 16 mg (N=)				
	Normal	Abn, Not CS ^[1]	Abn, CS ^[2]	Normal	Abn, Not CS ^[1]	Abn, CS ^[2]	Normal	Abn, Not CS ^[1]	Abn, CS ^[2]
12 Months									
Right		n			n			n	
Normal	n (%)	n (%)	n (%)	n (%)	n (%)	n (%)	n (%)	n (%)	n (%)
Abnormal, Not Clinically Significant	n (%)	n (%)	n (%)	n (%)	n (%)	n (%)	n (%)	n (%)	n (%)
Abnormal, Clinically Significant	n (%)	n (%)	n (%)	n (%)	n (%)	n (%)	n (%)	n (%)	n (%)
Left		n			n			n	
Normal	n (%)	n (%)	n (%)	n (%)	n (%)	n (%)	n (%)	n (%)	n (%)
Abnormal, Not Clinically Significant	n (%)	n (%)	n (%)	n (%)	n (%)	n (%)	n (%)	n (%)	n (%)
Abnormal, Clinically Significant	n (%)	n (%)	n (%)	n (%)	n (%)	n (%)	n (%)	n (%)	n (%)

Note: In the case of an early withdrawal, the result from the last retinal fundoscopy is considered for the 12 Months visit.

[¹] Abn, Not CS= Abnormal, Not Clinically Significant

[²] Abn, CS= Abnormal, Clinically Significant

path\t_program.sas date time

Table 22
Injection Site Reaction
Safety Population

	Placebo (N=)	VM202- 8 mg (N=)	VM202- 16 mg (N=)
Subject reported an Injection Site Reaction?			
Day 0 (Post-Dose)			
Yes	n n (%)	n n (%)	n n (%)
No	n n (%)	n n (%)	n n (%)
Day14 (Pre-Dose)			
Yes	n n (%)	n n (%)	n n (%)
No	n n (%)	n n (%)	n n (%)
Day14 (Post-Dose)			
Yes	n n (%)	n n (%)	n n (%)
No	n n (%)	n n (%)	n n (%)
Etc.			

path\t_program.sas date time

Programmer Note Repeat for all available time point, Day 28(pre- and post-dose), Day 42(pre- and post-dose), and Day 49(pre- and post-dose).

[figure not shown]
Table 23
Prior and Concomitant Medications
Safety Population

ATC Drug Class / Medication Term	Placebo (N=)	VM202- 8 mg (N=)	VM202- 16 mg (N=)
Subjects Receiving any Concomitant Medications	n (%)	n (%)	n (%)
Drug Class 1	n (%)	n (%)	n (%)
Medication Term 1	n (%)	n (%)	n (%)
Medication Term 2	n (%)	n (%)	n (%)
.	.	.	.
Drug Class 2	n (%)	n (%)	n (%)
Medication Term 1	n (%)	n (%)	n (%)
Medication Term 2	n (%)	n (%)	n (%)
.	.	.	.
Etc.			

Note: At each level of summation (overall, ATC drug class, medication term), subjects reporting more than medication are counted only once.
path\t_program.sas date time

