Treatment Group	Subject ID	Visit	Assessment Date (Study Day)	Reader 1 Score (mm)	Reader 2 Score (mm)	Comments
Placebo	xxxxxx	Visit	date9. (xx)	xxx	xxx	description
	xxxxxx	Visit	date9. (xx)	xxx	xxx	description
	...					
VM202- 8 mg	xxxxxx	Visit	date9. (xx)	xxx	xxx	description
	xxxxxx	Visit	date9. (xx)	xxx	xxx	description
	...					
VM202- 16 mg	xxxxxx	Visit	date9. (xx)	xxx	xxx	description
	xxxxxx	Visit	date9. (xx)	xxx	xxx	description
	...					

Note: Study Day = [(Date of Event) - (Treatment Start Date)]; 1 is added to the difference when 'Date of Event' is greater than or equal to 'Treatment Start Date'.
path\t_program.sas date time

Programmer note sort by assessment date within each subject.

Listing 19
Resting Transcutaneous Oxygen Pressure (TcPO₂) Measurements

Treatment Group	Subject ID	Visit	Date of Assessment (Study Day)	Anterior Chest (mmHg)	Dorsal Surface of Foot (mmHg)	Anterior Surface of Calf (mmHg)	Posterior Surface of Calf (mmHg)	Comments
Placebo	xxxxxx	Visit	date9. (xx)	result	result/Not Done	result/Not Done	result/Not Done	comments
		Visit	date9. (xx)	result	result/Not Done	result/Not Done	result/Not Done	comments
			...					
VM202- 8 mg	xxxxxx	Visit	date9. (xx)	result	result/Not Done	result/Not Done	result/Not Done	comments
		Visit	date9. (xx)	result	result/Not Done	result/Not Done	result/Not Done	comments
			...					
VM202- 16 mg	xxxxxx	Visit	date9. (xx)	result	result/Not Done	result/Not Done	result/Not Done	comments
		Visit	date9. (xx)	result	result/Not Done	result/Not Done	result/Not Done	comments
			...					

Note: Study Day = [(Date of Event) - (Treatment Start Date)]; 1 is added to the difference when 'Date of Event' is greater than or equal to 'Treatment Start Date'.
path\t_program.sas date time

Programmer note sort by date of assessment within each subject

Programmer note If No or Not Done is recorded on the CRF to indicate that TcPO2 measurements were not collected, show "Not Done" under the Date of Assessment column.

Listing 20
Resting Ankle Brachial Index (ABI) Measurements

Treatment Group	Subject ID	Visit	Date of Assessment (Study Day)	Brachial Systolic Pressure			Ankle Systolic Pressure - Right						Ankle Systolic Pressure - Left					

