Programmer note sort by date of assessment within each subject
Programmer note listing may need to be split over 2 pages.

Listing 22
Ulcer and Wound Assessment / Skin Condition Assessment

Treatment Group	Subject ID	Visit	Assessment Date (Study Day)	Does the Subject Have	Does the Subject Have	Skin Condition Assessment		
				Ulcers Present/Same Ulcer Still Existing?	New Ulcers NOT Present at Screening/Day 0?	Not Done	Scaling	Erythema
Placebo	xxxxxx	Visit	date9. (xx)	Yes/No	Yes/No		result	result
		Visit	date9. (xx)	Yes/No	Yes/No		result	result
			...					
			...					
VM202- 8 mg	xxxxxx	Visit	date9. (xx)	Yes/No	Yes/No		result	result
		Visit	date9. (xx)	Yes/No	Yes/No		result	result
			...					
			...					
VM202- 16 mg	xxxxxx	Visit	date9. (xx)	Yes/No	Yes/No		result	result
		Visit	date9. (xx)	Yes/No	Yes/No	Not Done		
			...					
			...					

Note: Study Day = [(Date of Event) - (Treatment Start Date)]; 1 is added to the difference when 'Date of Event' is greater than or equal to 'Treatment Start Date'.

Note: 0 = No Scaling/Erythema, 1 = Very Slight, 2 = Well-defined, 3 = Moderate to Severe, 4 = Severe.

path\t_program.sas date time

Programmer note sort by date of assessment within each subject

Listing 23
Ulcer Assessment

Treatment Group	Subject ID	Anatomical Location ^[1]	Visit Date (Study Day)	Visit	Ulcer Status			Comments
					Photo and Tracings Submitted to CPC	100% Healed		
Placebo	xxxxxx	1 or 2	date9. (xx) date9. (xx)	Screen Day 0 ...	result result	result result		comment comment
VM202- 8 mg	xxxxxx	1 or 2	date9. (xx) date9. (xx)	Screen Day 0 ...	result result	result result		comment comment
VM202- 16 mg	xxxxxx	1 or 2	date9. (xx) date9. (xx)	Screen Day 0 ...	result result	result result		comment comment

Note: Study Day = [(Date of Event) - (Treatment Start Date)]; 1 is added to the difference when 'Date of Event' is greater than or equal to 'Treatment Start Date'.

^[1] 1 = Vascular, 2 = Non-Vascular.

path\t_program.sas date time

Programmer note sort by time point within each subject.

Time points include Screen, Day 0, Day 14, Day 28, Day 42, Day 49, Day 90, 6 Month, 9 Month, 12 Month, USV #1, USV #2, USV #3, Early Exit.

Listing 24
Vascular Quality of Life (VascuQoL)
Part 1 of 2

Treatment Group	Subject ID	Visit	Was the VascuQoL Completed this Visit?	If Yes, Assessment Date (Study Day)	If No, Specify Reason:
Placebo	xxxxxx	Visit	Yes/No	date9. (xx)	description
	xxxxxx	Visit	Yes/No	date9. (xx)	description
	...				

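### Low-priority improvement: record VAS pain at early withdrawal, since the supporting ITT analysis carries the last VAS forward to month 9

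*Protocol*

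**What the plan says.** **What is collected at withdrawal.** Protocol 3.5.2 opens its list with "Subjects that withdraw prior to study completion will undergo the following if possible". Nine items follow: fundoscopy, concomitant medications, laboratory tests, ulcer photograph and measurement, vital signs, serum HGF, VM202 copies, injection-site assessment and adverse events. VAS is absent. In Protocol Appendix 1 the row "Visual Analog Scale (VAS) score" has ticks up to month 12 and none under Early Withdrawal. Protocol 4.2.7 names no VAS at withdrawal either.

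**What the analysis then uses.** For a missing 9-month score in the ITT population, SAP 10.1.2 first substitutes the month-12 score. Failing that, the rule is to "assign the last reported VAS prior to the 9 month VAS visit if both the 9 month and 12 month VAS assessments are missing". SAP 10.2.1.1 carries the previous post-baseline score forward for the by-visit VAS analyses.

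**Where ITT sits.** SAP 6 and 10 place the primary analysis in the per-protocol (PP) population, which requires an observed 9-month VAS. ITT contains everyone randomized and is additional. Protocol 6.2.1 also plans a secondary ITT analysis of the primary endpoint and further work if the two disagree.

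**Withdrawal values the plan does use.** Ulcers are on the withdrawal list, and the time points for SAP Listing 23 end with "USV #1, USV #2, USV #3, Early Exit". For fundoscopy, a safety measure, SAP 11.5 says: "If a 12 Month assessment was not performed, the last post-baseline assessment reported will be used". The note to Table 21 adds: "In the case of an early withdrawal, the result from the last retinal fundoscopy is considered for the 12 Months visit".

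**The concern.** PP drops anyone without a 9-month VAS, so ITT is the only planned analysis in which the pain of withdrawn subjects counts. For those subjects the 9-month value is normally a carried score, because someone who leaves before month 9 will have neither the 9-month nor the 12-month score.

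Such a subject may attend a withdrawal assessment without being asked to mark the pain line. The carried score then comes from the last scheduled visit, and any change in pain since that visit is lost. No later analysis can recover it.

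A subject who leaves before Day 14 has no post-baseline VAS at all. Read literally, SAP 10.1.2 would carry the baseline score (change of zero), while SAP 10.2.1.1 would have nothing to carry.

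**Working it through.** The plan gives no figure for this point and no dropout rate. Two things can be computed: how old the carried score can be, and how far one such score could move an arm mean.

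**1. Age of the carried score just before the next VAS visit.** Visits and windows are from Protocol Appendix 1. Nominal age = next visit − last visit. The oldest case sets the last visit at its earliest and the next at its latest. One month = 30.44 days.

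| Withdrawal between | Nominal | Oldest within windows |
|---|---|---|
| Day 14 and 28, or Day 28 and 42 | 14 days | (28+3) − (14−3) = 20 days |
| Day 42 and Day 90 | 90 − 42 = 48 days | (90+7) − (42−3) = 58 days |
| Day 90 and month 6 | 182.6 − 90 = 92.6 days = 3.0 months | (182.6+30.4) − (90−7) = 130 days = 4.3 months |
| Month 6 and month 9 | 3 months | (9+1) − (6−1) = 5 months |

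These are maxima. At mid-interval the nominal ages are half as large: 7 days, 24 days, 1.5 months and 1.5 months.

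**2. Standard error for scale.** SAP 4 assumes an SD of 25 mm for VAS change and arms of 20, 20 and 10. The standard error of a dose-placebo difference is 25 × √(1/20 + 1/10) = 9.68 mm.

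**3. One withdrawal after Day 90.** Assume d mm of change went unseen, with d from 10 to 20 (my assumption). The arm mean moves by d/n.

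- Placebo, n=10: 10/10 = 1.0 mm to 20/10 = 2.0 mm, or 0.10 to 0.21 standard errors.
- Dose arm, n=20: 10/20 = 0.5 mm to 20/20 = 1.0 mm, or 0.05 to 0.10 standard errors.

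Before the Day 90 follow-up, Protocol 3.5.2 replaces discontinued patients, but ITT keeps everyone randomized. If a replacement joins the same arm, the divisors become 11 and 21, giving 0.9 to 1.8 mm and 0.5 to 1.0 mm.

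**4. Whole-trial illustration.** Assumptions: 30-day months; withdrawal uniform over Days 0 to 270 at the same rate in each arm; effect accruing linearly to the SAP's planned high-dose minus placebo difference of 30 − 10 = 20 mm; a VAS obtained at every withdrawal.

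- The gaps between visits are 14, 14, 14, 48, 90 and 90 days. The mean age of the carried score is Σ(gap²/2)/270 = 35.4 days.
- The ITT difference at dropout rate p is 20(1 − p) + 20p × (135 − 35.4)/270 without a withdrawal VAS, and 20(1 − p) + 20p × 135/270 with one.

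| Dropout (assumed) | Without | With | Shift |
|---|---|---|---|
| 10% | 18.7 mm | 19.0 mm | 0.3 mm |
| 20% | 17.5 mm | 18.0 mm | 0.5 mm |
| 30% | 16.2 mm | 17.0 mm | 0.8 mm |

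The shift is 0.03 to 0.08 standard errors. Its direction follows from the assumed steady accrual. If withdrawal and unseen change are equal in the arms compared, the shift is 0 mm.

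**5. PP.** A withdrawal VAS is not a 9-month VAS, so it adds nobody to the PP population and changes nothing there.

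**The case against.** A reader might infer that VAS has been singled out for neglect, given how ulcers and fundoscopy are handled. The documents do not support that. VascuQol, ABI/TBI, TcPO₂ and Rutherford class also have no Early Withdrawal tick in Appendix 1, and SAP 10.2.2.1, 10.2.3.1, 10.2.6.1 and 10.2.8.1 carry them forward in the same way. Fundoscopy is a safety measure. Ulcer measurement is the one efficacy exception, and SAP 10.2.5 gives it no imputation rule. The withdrawal list is mainly a safety close-out, so adding VAS improves the plan; it does not repair an anomaly.

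Three further objections carry weight.

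- **A more recent score need not be closer to 9-month pain.** Protocol 4.2.7 asks for current pain, so the mark may reflect the event that prompted withdrawal and would still be carried to month 9. This stands.
- **Few subjects may benefit.** The assessment is done only where possible. The discontinuation reasons in the SAP Table 1 shell include death and loss to follow-up, which yield no mark. After a major amputation or limb-salvage procedure SAP 10.1.2 uses the earlier score anyway. Protocol 1.3.3 describes a population with about 25% mortality and 45% amputation-free survival at one year. This limits the gain, but the same shell lists adverse event, non-compliance, withdrawn consent and investigator decision, after which a subject could still attend.
- **The change is not free.** It needs a protocol amendment at up to twenty sites. This stands, and it keeps the priority low.

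SAP Table 2 also appears to have no withdrawal entry for VAS, but its columns do not align cleanly in the text available. The point therefore rests on Protocol 3.5.2, 4.2.7 and Appendix 1.

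**Conclusion.** The point holds as a cheap, low-priority improvement. VAS is not taken at early withdrawal, and the supporting ITT analysis carries the last scheduled score to month 9. That score can be up to about 3 months old at nominal visits, or 4.3 to 5 months within the windows.

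The likely effect is small: 0.5 to 2 mm on an arm mean per withdrawal after Day 90, if 10 to 20 mm of change went unseen, and 0.3 to 0.8 mm on a 20 mm difference in the illustration. The direction cannot be known in advance, and without a dropout rate the total effect cannot be sized.

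A reader might go further and conclude that the primary result is compromised or that ITT is biased in a known direction. Neither follows: PP is untouched, and nothing in the documents fixes the sign of the unseen change. VAS merits the addition because it measures the primary endpoint and needs a single mark.

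**What to change.** 1. Add VAS to the withdrawal list in Protocol 3.5.2, and tick it under Early Withdrawal in Protocol Appendix 1 and SAP Table 2.
2. SAP 5.1 analyses data by nominal visit, so the use of the new score must be written down. State in SAP 10.1.2 and 10.2.1.1 that the early-withdrawal VAS counts as the last reported VAS for every scheduled VAS visit missed after withdrawal. For example, it would serve Day 90 and months 6, 9 and 12 if withdrawal falls between Day 42 and Day 90. The existing amputation and limb-salvage rules take precedence.

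**Cost.** A protocol amendment with any IRB review it needs, one CRF field, one mark at an assessment already planned, and the usual scoring of "where the subject places the perpendicular line by two independent readers" (SAP 10.1). The SAP wording changes in two sections.

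**Separate editorial note, not part of the support for this point.** SAP 10.1.2 and 10.2.1.1 overlap when month 9 is missed and month 12 is present: the first uses month 12, the second the earlier score. The 9-month VAS shells for ITT all cite 10.1.2, so the planned tables would not show two different results. Still, 10.2.1.1 should exclude month 9, and shells 5.1.2, 5.2.2 and 5.4.2 should cite 10.2.1.1 for the other six visits, for which 10.1.2 has no missed-visit rule.
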